## 6.3 Serious Adverse Events

Serious adverse events (SAEs) will be defined per CFR 312.32 guidelines, as AEs occurring at any dose that:

- Result in death;
- Are life-threatening adverse events;
- Require inpatient hospitalization or prolongation of existing hospitalization;
- Result in persistent or significant disability/incapacity; or
- Are congenital anomalies/birth defects.

Important medical events that may not result in death, be life-threatening, or require hospitalization may be considered serious when, based upon appropriate medical judgment, they may jeopardize the participant or require medical or surgical intervention to prevent one of the outcomes listed above.

Note: All SAEs must be reported on the AE Log CRF.

### 6.3.1 Grading System

All AEs will be graded using the DAIDS AE Grading Table, Version 1.0, December 2004 (Clarification dated August 2009) and the DAIDS Addendum 2 - Male Genital Grading Table, which are available at <http://rsc.tech-res.com/safetyandpharmacovigilance/>. Grade 1 creatinine toxicity will be determined by either the DAIDS AE Grading Table OR Grade 1 as defined by creatinine > 1.5x the participant's baseline serum creatinine, whichever is higher."

### 6.3.2 Assessment of Relationship to Study Agent

The relationship of all AEs to FTC/TDF will be assessed per the package insert and investigator's brochure for FTC/TDF, and clinical judgment of the investigator. The relationship categories that will be used for this study are related and not related, as defined in the Manual for Expedited Reporting of Adverse Events to DAIDS (Version 2.0, dated January 2010) which is available at <http://rsc.tech-res.com/safetyandpharmacovigilance/>.

## 6.4 Reporting Requirements for this Study

The Serious Adverse Event (SAE) Reporting Category, as defined in Version 2.0 (or latest version) of the DAIDS EAE manual, will be used for this study. The study agents for the purposes of SAE reporting are part of a fixed dose combination tablet: emtricitabine (FTC)/tenofovir disoproxil fumarate (TDF).

The SAE reporting period for this study is per the DAIDS EAE manual and continues from enrollment of a trial participant to the end of trial follow-up for that participant. All reportable SAEs occurring during the study reporting period will be reported to the principal investigator in an expedited manner, within three reporting days of site awareness of the events (see definition in Appendix D of the DAIDS EAE Manual).

Reporting requirements for the local IRB will also be followed.

## **6.5 Social Harms Reporting**

Although study sites will make every effort to protect participant privacy and confidentiality, it is possible that participants' involvement in the study could become known to others, and that social harms may result. For example, participants could be perceived as being HIV-infected or at high risk for HIV infection and be treated unfairly or have problems being accepted by their families and/or communities. Social harms that are judged by the PI/designee to be serious or unexpected will be reported to the responsible site's IRB at least annually, or according to its individual requirements.

Social harms will be collected and reported on CRFs during regular visits. In the event that a participant reports social harm, every effort will be made by study staff to provide appropriate care and counseling to the participant, and/or referral to appropriate resources for the safety of the participant. Each site will provide such care and counseling in accordance with standardized guidance in the SOP.

## **6.6 Toxicity Management**

The site clinician has the discretion to hold FTC/TDF at any time if s/he feels that continued medication use would be harmful to the participant or interfere with treatment deemed clinically necessary according to the judgment of the investigator. Clinical or laboratory abnormalities that require follow up will be documented, and the research associate or clinician will contact the participant to schedule an interim visit for follow-up and/or repeat laboratory testing. All participants reporting an adverse event will be followed clinically until the occurrence resolves (returns to baseline grade, defined as grade at enrollment) or stabilizes or an effective referral to local health care providers is accomplished.

### **6.6.1 Discontinuation of Study Medication**

#### Grades 1 or 2

Continue FTC/TDF at the discretion of the site investigator.

#### Grade 3

FTC/TDF may be continued at the discretion of the site investigator if a Grade 3 toxicity is considered to be unrelated to the study medication. Study medication will be temporarily withheld if Grade 3 toxicity is considered to be related to the study medication. After a Grade 3 toxicity returns to Grade 1, the participant can be reintroduced to medication after consultation with the site investigator, DAIDS Medical Officer, and other members of the CMC. If a Grade 3 toxicity recurs and is considered to be related to study medication, FTC/TDF will be permanently discontinued.

#### Grade 4

For all Grade 4 laboratory-identified or clinical toxicities, FTC/TDF will be withheld unless it is determined to be not related. If a Grade 4 laboratory toxicity is not confirmed by repeat testing, it should be managed per algorithm for the new toxicity grade. Participants with Grade 4 AEs will be followed until the event resolves to baseline or stabilizes. Study drug may be restarted in the event of the resolution of a Grade 4 AE back to Grade 1, after consultation with the site investigator, DAIDS Medical Officer, and other members of the CMC. If the toxicity recurs to Grade 3 or higher after FTC/TDF is restarted and is considered to be related to FTC/TDF, the study medication will be permanently discontinued.

### **6.6.2 Creatinine Elevations**

For creatinine elevations >1.5-fold above baseline creatinine (at screening), serum creatinine will be repeated as soon as possible, preferably within 7 days. Participants who fail to have a confirmed test within two weeks of receiving the initial result should be permanently discontinued from use of the study drug and the CMC should be notified. FTC/TDF will be held for confirmed creatinine elevations >1.5-fold

above baseline until creatinine returns to <1.3-fold above baseline, at which point the participant may be re-challenged with FTC/TDF after consultation with the site investigator. Clinicians may re-test creatinine levels more often (i.e., weekly) should they choose; however, after the initial re-test approximately 7 days later, it is not required per protocol to re-test serum creatinine until the next scheduled study visit. If serum creatinine rises again to >1.5-fold above baseline when drug is restarted, the CMC must be notified and FTC/TDF should be permanently discontinued and the participant will be monitored as deemed clinically appropriate in consultation with the CMC until level returns to baseline (screening value) or stabilizes.

### 6.6.3 Creatinine Clearance

- Estimated CrCl < 60 mL/min

If the calculated creatinine clearance is <60 mL/min, it should be confirmed ideally within approximately one week of the receipt of the results.

**Discontinue study drug temporarily. Participants who fail to have a confirmed test within two weeks of receiving the initial result should be permanently discontinued from use of the study drug and the CMC should be notified.**

- Confirmed CrCl < 60 mL/min

If the calculated creatinine clearance is confirmed to be <60 mL/min, the study drug must be temporarily discontinued. As previously stated, participants who fail to have a confirmed test within two weeks of receiving the initial result should be permanently discontinued from use of the study drug and the CMC should be notified. The participant will be monitored as deemed clinically necessary in consultation with the CMC until level returns to baseline (screening value) or stabilizes.

**Temporarily discontinue study drug (unless the participant does not return for repeat testing within approximately two weeks).**

- Re-testing result is  $\geq 60$  mL/min

If re-testing yields a result  $\geq 60$  mL/min, the Investigator may re-start study drug use, and follow creatinine clearance over time as deemed clinically necessary.

## 6.7 Concomitant Medications

With the exception of medications listed as prohibited (see below, this section), enrolled study participants may use concomitant medications during study participation. All concomitant medications, including prescribed and over-the-counter preparations, vitamins and nutritional supplements, recreational drugs and herbal preparations reported within 45 days prior to confirmation of eligibility for study enrollment and throughout the course of the study will be recorded on the CRF designated for that purpose. Medications used for the treatment of AEs that occur during study participation will also be recorded on applicable study CRFs. Participants who begin taking any medication during the trial that is listed as an exclusionary medication at Screening will temporarily discontinue study drug. Study drug may be resumed if no exclusionary medication has been taken in the last 4 weeks, if serum creatinine is within 1.3-fold above baseline, and if HIV testing is non-reactive/negative.

Should participants report use of any of the following medications, they will be required to discontinue use of study drug: interleukin therapy, medications with significant nephrotoxic potential (including but not limited to amphotericin B, aminoglycosides, cidofovir, foscarnet and systemic chemotherapy), and medications that may inhibit or compete for elimination via active renal tubular secretion (including but not limited to probenecid).

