### 5.3 Month 1, 3 and Month 6 (exit visit)

At months 1 and 3, the participants will visit the clinical site to complete the assessments and receive the medication supply for next two (at month 1) three (at month 3) months. At month 6, participants will not receive medication as a part of the study, but will be referred to other available PrEP providers in Kyiv. The following procedures will be included.

- Verify locator information
- Behavioral and psychosocial survey
- Self-reported study product adherence assessment
- PrEP discussion
- PrEP Navigation and study product supply
- Autonomy supportive adherence counseling
- SMS reminder customization

- HIV/ STI behavioral risk-reduction counseling, provision of prevention supplies
- Medical history including but not limited to co-morbidities, concomitant medications, HIV risk history
- Symptom-driven physical exam
- AE Assessment
- HIV rapid test – at months 3 and 6.
- DBS storage for pharmacology testing
- Urine storage for substance use testing

The exit visit will include all procedures for Month 3, except for PrEP provision and related counseling and SMS customization.

#### 5.4 Months 2, 4, 5

Monthly assessments between the PrEP dispensing visits (Enrollment and 3-month) will be conducted by research staff **by telephone**. The following procedures will be included.

- Review and update locator information
- Self-reported study product adherence assessment

Self-reported PrEP adherence for all participants will be assessed using both a visual analogue scale (VAS) and a new 3-item self-report measure. The VAS is empirically validated, consistently under-reports adherence, but effectively measures a “difference” in adherence that changes in response to an intervention. The 3-item adherence self-report scale showed good psychometric characteristics and good construct validity when compared with an drug monitoring standard. Two self-report adherence measures are often recommended.

- PrEP discussion
- Autonomy supportive adherence counseling
- SMS reminder customization

Experimental arm participants will have an opportunity to change the parameters of the SMS reminders.

- HIV/ STI behavioral risk-reduction counseling

After the standard risk-reduction counseling, the participants will be invited to visit the harm reduction site to receive supplies.

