#### PrEP persistence

PrEP persistence is defined as the time from PrEP start to PrEP discontinuation. A PrEP discontinuation is considered to have occurred if a participant self-reported to miss the PrEP doses for 30 or more consecutive days, for reasons other than a medication hold instituted by a clinician.

**Secondary Endpoints:** The secondary endpoints of this study include the following:

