**APPENDIX I - SCHEDULE OF EVALUATIONS AND PROCEDURES**

	Pre-screening	Enrollment	Month 1, 3	Month 2,4,5 (by phone)	Month 6 (exit)	Interim visits
Administrative and Behavioral Evaluations/ Procedures						
Pre-screening	x					
Eligibility screening and demographic information		x				
Informed Consent, randomization		x				
Locator information		x	x	x		x
Behavioral and psychosocial survey		x	x		x	
Initial PrEP adherence readiness assessment (PN)		x				
Self-reported study product adherence assessment (PN)			x	x	x	x
Individual Interview for selected participants						x
Staff Focus Group (after all participants complete)						x
Intervention provision						
PrEP Discussion		x	x	x	x	x
Autonomy Supportive Adherence Counseling		x	x	x		x
PrEP Navigation and study product supply		x	x			x
SMS reminder customization 		x	x	x		x
SMS reminder 		x	xx	xx		
HIV/ STI behavioral risk-reduction counseling		x	x		x	x
Provision of prevention supplies		x	x		x	x
Clinical Evaluations/ Procedures						
Medical history including medications		x				
Symptom-Driven Physical Examination		x				
Laboratory Evaluations/Procedures						
HIV screening testing		x	x 		x	
HBsAg testing		x			x	
Renal function tests (creatinine)		x				
Calculated creatinine clearance		x				
DBS storage for possible Pharmacology testing		x	x		x	

 Experimental arm only.

 Month 3 only

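### Section 6.7 relies on concomitant medications being reported throughout, but Appendix I and Section 5.3 disagree on when they are asked about, and no scheduled contact asks during the Month 3 to 6 supply

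*Protocol*

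**What the plan says.** Protocol Section 6.7 states that concomitant medications reported in a window before enrollment and "throughout the course of the study will be recorded on the CRF designated for that purpose". It then names a group of medicines, including those that can damage the kidney or compete for tubular secretion, and sets the rule: "Should participants report use of any of the following medications, they will be required to discontinue use of study drug". The trigger is a report by the participant.

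Three places govern when that report is sought.

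- Appendix I has a row "Medical history including medications" with a single mark, under Enrollment. The columns for Months 1 and 3, Months 2, 4 and 5, Month 6 and interim visits are empty.
- Section 5.3 lists "Medical history including but not limited to co-morbidities, concomitant medications, HIV risk history" among the procedures for Months 1, 3 and 6. It keeps the item at Month 6: "The exit visit will include all procedures for Month 3, except for PrEP provision and related counseling and SMS customization".
- Section 5.4, on the telephone contacts at Months 2, 4 and 5, lists locator update, self-reported adherence, PrEP discussion, adherence counseling, SMS customization and risk-reduction counseling. It has no medication, medical history or adverse event item.

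On supply, Section 5.2 gives one month of drug at Enrollment. At the next clinic visits participants "receive the medication supply for next two (at month 1) three (at month 3) months". Then: "At month 6, participants will not receive medication as a part of the study".

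**The concern.** A rule triggered by a participant's report works only as well as the asking. Two things weaken it here. First, the schedule table and the visit text give different answers on whether anyone asks after Enrollment, and a site working from the table would not ask again. Second, even the fuller version in Section 5.3 leaves the longest supply interval without a scheduled question. The Month 6 question comes when that supply is due to have run out, too late to act on a listed medicine taken alongside it.

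What is at stake is a safety procedure that the protocol itself set up, and the completeness of the concomitant-medication record that Section 6.7 promises. Laboratory monitoring does not fill the gap. Appendix I marks creatinine and creatinine clearance at Enrollment only, and Section 5.3 lists no renal test at Months 1, 3 or 6. The one scheduled exception is Section 5.6, which requires creatinine from people restarting PrEP at Month 3.

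**Working it through.** The protocol gives no figure to reproduce. The check counts scheduled contacts and compares them with the dispensing intervals.

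**Inputs.** Scheduled contacts are Enrollment and Months 1 to 6, so 1 + 6 = 7 (Sections 5.2 to 5.4). Supplies are 1 month at Enrollment (Section 5.2), 2 months at Month 1 and 3 months at Month 3 (Section 5.3), so 1 + 2 + 3 = 6 months. The last supply covers Months 3 to 6.

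| Contact | Medication item, Appendix I | Medication item, Sections 5.2 to 5.4 |
|---|---|---|
| Enrollment | yes | yes |
| Month 1 | no | yes |
| Month 2 (phone) | no | no |
| Month 3 | no | yes |
| Month 4 (phone) | no | no |
| Month 5 (phone) | no | no |
| Month 6 | no | yes |
| Total | 1 of 7 | 4 of 7 |

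**Intervals without a question.**
- Appendix I: from Enrollment to the end, 6 of 6 months.
- Section 5: 1 − 0 = 1 month, 3 − 1 = 2 months and 6 − 3 = 3 months.

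**During the last supply.** The only scheduled contacts strictly inside Months 3 to 6 are Months 4 and 5. Under both versions 0 of 2 ask. That interval is 3/6 = 50% of follow-up and of the drug supplied.

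**Eligibility against the stopping rule.** The only medication exclusion in Section 3.2 is recent antiretroviral use (PrEP or PEP). The medicines listed in Section 6.7 do not appear there. Someone already taking one can meet every named criterion and still fall under the stopping rule.

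**Two stopping instructions within Section 6.7.** For medicines that were exclusionary at Screening, the text calls for a temporary stop and gives conditions for resuming. For the separately listed medicines it requires a stop and does not say whether or when drug may be resumed.

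**After the fix below.** Adding the item to the three calls gives 4 + 3 = 7 of 7 contacts. The longest interval without a question falls from 3 months (Section 5) or 6 months (Appendix I) to 1 month.

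**The case against.** The strongest reply is that Section 5.0 calls Appendix I an overview and puts the visit detail in Section 5, so Section 5.3 should be followed. The question is then asked at Months 1 and 3 while drug is still to be taken. This is reasonable, but the protocol does not say which text governs, and it leaves the Month 3 to 6 gap untouched.

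The rule also needs only a report, and there are unscheduled routes for one: interim visits at any time with navigator triage and outside visits found through the health information exchange (Section 5.5), records from non-study providers (Section 6.2), serious adverse event reports including hospitalizations (Sections 6.3 and 6.4), and anything volunteered in the telephone PrEP discussion. SOPs and the medication CRF, which are not available here, may prompt further. This argument stands against one tempting inference, that the stopping rule cannot operate at all. It can. What is missing is scheduled asking.

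On eligibility, item 13 of Section 5.2 requires the clinician to check for contraindications and drug interactions before PrEP. Section 3.2 also excludes conditions that staff judge unsafe, and participants may be enrolled without taking drug. These largely cover the mismatch in practice, so what remains is a need to align the lists.

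A reader might also infer that persistence or dried-blood-spot adherence is biased. The documents do not support this. If a listed medicine is never reported, the protocol triggers no stop, so the unasked question produces no missed doses. If it is reported, the reason for stopping is known, and the persistence definition already sets aside gaps "for reasons other than a medication hold instituted by a clinician". The surveys also ask why people stopped (Section 7.1).

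**Conclusion.** The point holds as a scheduling contradiction and a gap in a safety procedure. Section 6.7 requires recording throughout and makes a stop depend on reported use. Appendix I and Section 5.3 disagree on whether the question is asked after Enrollment, and Section 5.4 does not include it. Scheduled detection is absent for all 6 months after Enrollment if Appendix I is followed, and absent while the Month 3 to 6 supply is taken (0 of 2 contacts, half of follow-up) under either version.

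The number of participants affected cannot be estimated, because the protocol gives no figure for use of the listed medicines. The conclusion assumes that the single mark in the Appendix I row belongs to Enrollment. The table was read from PDF, but the mark lines up with those for physical examination and creatinine. It also assumes that SOPs do not already add the question to the calls. Even if they do, the contradiction between the two protocol passages remains. Neither the primary analysis nor the validity of the trial is in question on this point.

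**What to change.** 1. Bring Appendix I into agreement with Sections 5.3 and 6.7 by marking concomitant medications at Months 1, 3 and 6 and at interim visits.
2. Add one concomitant-medication question to the existing Month 2, 4 and 5 calls in Section 5.4 and the matching Appendix I column. Pass any positive answer to the site clinician, to be handled under Section 6.7.
3. Ask the investigators to reconcile the Section 3.2 exclusions with the Section 6.7 list, taking account of the clinician check already in item 13 of Section 5.2.
4. Ask the investigators to reconcile the two stopping instructions in Section 6.7. Which should apply, and how a resulting stop is to be classified, is for them to decide.

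The cost is a table correction, some editing and about a minute per call. With three calls per participant and 200 participants, that is at most 3 × 200 = 600 minutes, or about 10 staff hours over the trial. No new visit or sample is needed.

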## 7.0 STATISTICAL CONSIDERATIONS

### 7.1 Review of Study Design

This is an open-label, two-site, two-arm, prospective, randomized controlled trial that aims to assess the initiation, acceptability, safety, and feasibility of daily PrEP for PWID in Ukraine with or without SMS reminder intervention. HIV-uninfected PWID aged 18 and over and at risk for HIV infection will be

recruited and enrolled. Each participant will be offered daily PrEP and followed up to 6 months.

Participants will be followed at the specified study time points and will be evaluated for side effects, adherence, risk behavior and HIV-seroconversion.

**Primary Endpoints:** The primary endpoint of this study is the adherence to PrEP.

#### PrEP adherence

Adherence will be assessed via self-report (VAS and 3-item screener) and TDF concentration in DBS samples. TDF will be quantified with a validated liquid chromatography tandem mass spectrometry method.

#### PrEP persistence

PrEP persistence is defined as the time from PrEP start to PrEP discontinuation. A PrEP discontinuation is considered to have occurred if a participant self-reported to miss the PrEP doses for 30 or more consecutive days, for reasons other than a medication hold instituted by a clinician.

**Secondary Endpoints:** The secondary endpoints of this study include the following:

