PrEP efficacy in both MSM and PWID in RCTs reduces HIV transmission by ~50%. Adherence, however, is the key factor contributing to its success. For example, in the IPrEx study in MSM, self-reported adherence was 51%, though dried blood testing (DBS) suggested it as being only 41%. Similarly, in the Bangkok Tenofovir Study (BTS), self-reported adherence was 67%, though daily supervised monitoring confirmed only 49% adherence. In the BTS, an open-label extension of 793 PWID, showed low overall adherence to daily PrEP; almost half (47%) had less than 10% adherence, but only 25% had high (>90%) adherence. PrEP in the BTS was supervised daily at methadone clinics and during incarceration, and being incarcerated was independently associated with higher levels of adherence, suggesting that without daily monitoring, PrEP adherence in the community will likely be lower. Moreover, subsets of MSM in PrEP trials had underlying substance use disorders, yet the efficacy of PrEP or adherence levels among them is unknown. In the BTS, all PWID on the trial were maintained on methadone and the analysis did not disaggregate efficacy or adherence for the subgroup that continued to inject. Consequently, it is crucial to better understand adherence to daily PrEP in subgroups of MSM and PWID with substance use disorders who have suboptimal adherence to PrEP, but who are the ones who likely need it most.

Adherence guidelines by the International Association of Physicians in AIDS Care describes adherence optimization strategies, including in key populations like patients with substance use disorders. Though these guidelines do not include PrEP, recommendations for PrEP adherence are likely to apply. Short-messaging service (SMS) or text messaging is recommended, including from a systematic review of reviews that supports SMS use and recommends refinements in frequency and message content. Another systematic review in patients with HIV confirmed the adherence benefits from using SMS and extended it to improvements in clinic attendance, which is crucial for PrEP monitoring every three months. Moreover, while SMS works generally, two-way interactive and tailored reminders appear to be most beneficial, but can be burdensome to patients if too frequent.

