## 7.2 Sample Size Consideration

A total sample size of 200 PWID participants will be recruited into the study. Each participant will be enrolled to receive daily PrEP with Navigation for at least 6 months. Half of them will be randomized to receive SMS reminders.

For the PrEP adherence endpoint, the adjacent table lists the two-sided 95% confidence intervals for the true percentage of the PrEP adherence rates for the PWID who actually receive PrEP, assuming a 10% to 20% loss-to-follow-up (e.g. including those lost due to incarceration) during the 6-month period. For example, if the PrEP acceptance rate is 50% and an observed adherence rate is 67%, then there is 95% chance that the range 58%-76% will contain the true PrEP adherence rate.

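### PrEP discontinuation is triggered only by a self-reported 30-day gap, so participants lost without reporting one can never be events and persistence is open to informative loss

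*Protocol*

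**What the plan says.** Section 7.1 states that "PrEP persistence is defined as the time from PrEP start to PrEP discontinuation", and then gives the event: "A PrEP discontinuation is considered to have occurred if a participant self-reported to miss the PrEP doses for 30 or more consecutive days". The only qualification is that holds ordered by a clinician do not count. The definition comes before the list of secondary endpoints. Persistence (Schema) or retention (Section 2.1) is part of the primary objective, to be compared between arms, and Section 7.3.1 analyses it under Primary Analyses with Kaplan-Meier plots of time to first discontinuation.

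The scheduled supply is limited. Section 5.2 provides one month of tablets at enrollment. Section 5.3 has participants attend at Months 1 and 3 and "receive the medication supply for next two (at month 1) three (at month 3) months". Appendix I also marks product supply at interim visits.

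On loss, Section 7.2 works from 200 participants, "assuming a 10% to 20% loss-to-follow-up (e.g. including those lost due to incarceration) during the 6-month period". Section 5.7 adds that the data of anyone who chooses to withdraw are deleted and not analysed.

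**The concern.** The event can be recorded only from someone who is still in contact and who reports the gap. The participants most likely to have stopped include those who no longer attend or answer the phone, and the definition gives them no route to becoming an event. Standard Kaplan-Meier handling censors them, which treats them as having the same future risk of stopping as those still followed. For someone who has missed a dispensing visit and received nothing since, that is hard to defend.

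The other measures in the protocol do not close this gap. The medication possession ratio in Section 7.3.1 is restricted to those continuing on PrEP, so it depends on the same event. The dried blood spot (DBS) comparison in Sections 7.3.1 and 7.3.2 concerns agreement between adherence measures, not discontinuation.

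At stake are the absolute level of persistence and the comparison of persistence between the SMS and usual arms.

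**Working it through.** **No stated figure to reproduce.** The protocol gives no event count, power or hazard ratio for persistence. Its only sizing is the precision of an adherence percentage, so the check below asks how far the definition could move the persistence estimate.

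**When supply runs out (Sections 5.2 and 5.3, Appendix I)**
- Misses Month 1, no interim supply: tablets end about 1 month after the start.
- Attends Month 1, misses Month 3, no interim supply: tablets end at 1 + 2 = 3 months.
- Attends Month 3: scheduled supply lasts 1 + 2 + 3 = 6 months, to the exit visit.

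In the first two cases the definition still records nothing unless the participant reports a gap.

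**Inputs**
- Total 200, allocated 1:1 (Schema, Section 7.2).
- Loss L = 10% or 20% (Section 7.2), that is 20 or 40 people.
- True six-month persistence S = 33%, 50% or 67%, the scenarios in the Section 7.2 table.

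**Case A, informative loss (assumption).** Everyone lost has stopped PrEP, is lost at the time of stopping, and reports no gap. The fraction of stoppers who go unrecorded is p = L / (1 − S). If p does not vary over time, the recorded hazard is (1 − p) times the true hazard, so Kaplan-Meier estimates S^(1 − p). For S = 50% and L = 20%: p = 0.20 / 0.50 = 0.40, and 0.50^0.60 = 0.660.

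| True S | L | p | Kaplan-Meier | Overstatement (points) |
|---|---|---|---|---|
| 33% | 10% | 0.149 | 38.9% | 5.9 |
| 33% | 20% | 0.299 | 45.9% | 12.9 |
| 50% | 10% | 0.200 | 57.4% | 7.4 |
| 50% | 20% | 0.400 | 66.0% | 16.0 |
| 67% | 10% | 0.303 | 75.6% | 8.6 |
| 67% | 20% | 0.606 | 85.4% | 18.4 |

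A simulation with 100,000 subjects per scenario and exponential stopping times gave 39%, 46%, 58%, 66%, 76% and 86% in the same order. Subtracting those rounded values puts the top of the range at 19 points; unrounded, it is 18.

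**Case B, loss independent of stopping.** The same simulation returned Kaplan-Meier values of 33%, 50% and 67% at both loss rates, so there was no bias.

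**Between arms, under Case A.** The split of loss by arm is assumed; the protocol gives none.

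| True control / SMS | Loss control / SMS | Kaplan-Meier control / SMS | Apparent difference (points) |
|---|---|---|---|
| 40% / 50% | 20% / 10% | 54.3% / 57.4% | 3.1 |
| 40% / 50% | 15% / 15% | 50.3% / 61.6% | 11.3 |
| 40% / 50% | 10% / 20% | 46.6% / 66.0% | 19.4 |
| 50% / 60% | 20% / 10% | 66.0% / 68.2% | 2.2 |
| 50% / 60% | 15% / 15% | 61.6% / 72.7% | 11.1 |
| 50% / 60% | 10% / 20% | 57.4% / 77.5% | 20.0 |
| 50% / 50% | 20% / 10% | 66.0% / 57.4% | −8.5 |
| 50% / 50% | 10% / 20% | 57.4% / 66.0% | +8.5 |

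A true 10-point benefit can read as 2 to 3, about 11, or about 20 points. With no true difference, unequal loss alone can produce an apparent one of about 8.5 points in either direction.

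**The case against.** Several points on the other side stand.

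- **Some gaps are caught before loss.** Adherence is assessed monthly (Sections 2.3 and 5.4) and tracers make in-person contact (Section 3.4). A reader might infer that lost participants never count as discontinued; in fact only those who reported no 30-day gap beforehand are missed.
- **Handling of losses may be in the SAP.** Section 7.3.1 gives no censoring rule, and that is normal. But an SAP censoring rule would leave the Section 7.1 event definition as it is, and the definition is the problem.
- **A hidden SMS effect is not shown.** Section 1.1 cites better clinic attendance with SMS in patients with HIV, so one might give 10% loss to the SMS arm and 20% to control and conclude that a benefit disappears. The protocol uses 10% and 20% as alternative overall scenarios, not arm rates, and the reverse split inflates the difference.
- **Self-report is not wholly unchecked.** DBS is compared with self-reported adherence and a possession ratio is planned. Neither enters the discontinuation event.
- **The VAS statement is not shown to be wrong.** Section 5.4 says "The VAS is empirically validated, consistently under-reports adherence", whereas Section 1.1 reports for one trial that "self-reported adherence was 67%, though daily supervised monitoring confirmed only 49% adherence". These are in tension, but Section 1.1 does not name the self-report instrument. Its percentages also measure adherence, so the gap cannot be carried over to under-reporting of a 30-day interruption.
- **Loss is not always stopping.** Section 7.2 includes incarceration in loss, and Section 1.1 associates incarceration with higher adherence in a cited trial. Tablets may also be obtained at interim visits or elsewhere.

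**Conclusion.** The definition is deficient for an outcome in the primary objective: a participant lost without first reporting a 30-day gap cannot be an event, even after exhausting all dispensed tablets. At the protocol's own 10% to 20% loss, persistence is overstated by about 6 to 18 points if all those lost have stopped PrEP, and not at all by Kaplan-Meier if loss is unrelated to stopping. The first condition is plausible for people who miss a dispensing visit, but the documents do not establish it. The direction of any bias between arms is unknown.

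This is should-fix rather than must-fix. Section 7.1 names adherence as the primary endpoint, and its binary outcome in Section 7.3.1 is a DBS threshold that this definition does not affect.

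**What to change.** In Section 7.1, define discontinuation for analysis as the earlier of:

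- (a) a self-reported gap of 30 or more consecutive days; or
- (b) 30 days past exhaustion of all dispensed supply, counting scheduled and interim visits, with no refill and no contact confirming use, dated to supply exhaustion.

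Keep clinician-instituted holds excluded, as now. Report two sensitivity analyses: the self-report-only definition, and a version that censors participants known to be incarcerated.

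Use Month 3 and Month 6 DBS results, where tested, only as a supportive check on reported continuous use. They should not define an event: Section 5.2 allows testing of a subset only, a visit result gives no event date, and lost participants give no sample.

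Reconcile the rule with Section 5.7, since deleting withdrawers' data removes them from any persistence analysis. Clarify the VAS statement in Section 5.4 against the self-report figures in Section 1.1.

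The cost is endpoint wording and programming from dispensing records. A few participants using leftover or outside tablets will be counted as discontinued, and reported persistence will be somewhat lower. The supply rule cannot detect stopping after the Month 3 dispensing, because that supply runs to the exit visit; self-report remains the only trigger there. The change should be made before arms are compared, since a definition chosen later would be open to challenge.
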